Additionally, there is and will remain practice variations in catheter placement. While we hope to find a difference despite these differences, it is possible that the intervention may give a false impression of improvement simply by focusing attention on a protocol. While it is difficult to remove confounding from any study, randomization and analysis adjustments will be used to reduce as much as possible.

VI. Data Analysis Plan:

This study will assess a population of patients undergoing extended surgery requiring catheter placement to be performed by the Gynecologic Oncology service. De-identified patient data will be collected into OnCore and exported to SPSS for data analysis. Initial summary statistics will be performed to report the distribution of the data, including variable means, medians, proportions and missing data.

An intent-to-treat analysis will be conducted. All participants receiving treatment per protocol will be included in the final analysis. If there are any participants who are randomized but do not receive the intended treatment, we will document the reasons for their being withheld treatment.

For the primary outcome measure of UTI rate at each of the time points (24 hours and 14 +/- 2 days), we will perform a test of binomial proportions for testing the null hypothesis of no difference between the treatment arms. Because we are performing tests at two time points, we will adjust for the multiple comparisons using Bonferroni's method.

We will also explore the association between treatment arms and other covariates (symptomatic and demographics factors) using bivariate methods. The particular analysis method for testing the association between them will depend on the distribution of the covariates. For example, symptomatic presentation variables (fever, pelvic pain, sense of urgency or dysuria, and antibiotic use) are categorical, and their association with treatment arm will be evaluated with a chi-square statistic.

For demographic variables, Student's *t*-test (for continuous variables) and chi-square tests (for categorical variables) will be used to compare the two treatment arms. Variables found to be significant in these bivariate analyses will be included in multivariable analysis using logistic regression. Logistic regression models will be used to identify significant independent predictors associated with UTI

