occurrence for each treatment arm. We will fit separate logistic regression models for UTI occurrence at the two time points. The logistic model will allow for control of study covariates simultaneously. A p-value of <0.005 will be used to demonstrate statistical significance. IBM SPSS version 23 will be used for all statistical analyses.

Secondary outcomes will include a cost-analysis of the two treatment protocols and a patient satisfaction query in regards to the catheter procedure.

- Cost-analysis: The cost-effectiveness of the interventions will be assessed using hospital stay, readmissions, clinic/ED visits, and antibiotic costs per patient during the study period. An estimate of patient care costs will be derived using standard cost data described in the literature. The two groups will be compared in terms of average cost of treatment with a 95% confidence interval using a Bayesian statistic.
- Satisfaction: Patient satisfaction with the catheter protocol will be measured using a Likert-like scale questionnaire. Responses between the two groups will be compared using a Mann-Whitney-Wilcoxon statistic.

VII. Summarized Knowledge to be gained:

This study aims to reduce the incidence of urinary tract infections in patients undergoing surgery on the Gynecologic Oncology service through an aseptic protocol for placement. Such quality improvement studies are needed to help reduce complication rates and health-care costs.

VIII. References:

1. Septimus, E.J. and J. Moody, *Prevention of Device-Related Healthcare-Associated Infections*. F1000Res, 2016. **5**.
2. Stephan, F., et al., *Reduction of urinary tract infection and antibiotic use after surgery: a controlled, prospective, before-after intervention study*. Clin Infect Dis, 2006. **42**(11): p. 1544-51.
3. Barbadoro, P., et al., *Catheter-associated urinary tract infection: Role of the setting of catheter insertion*. Am J Infect Control, 2015. **43**(7): p. 707-10.
4. Amine, A.E., M.O. Helal, and W.M. Bakr, *Evaluation of an intervention program to prevent hospital-acquired catheter-associated urinary tract infections in an ICU in a rural Egypt hospital*. GMS Hyg Infect Control, 2014. **9**(2): p. Doc15.
5. Singh, S., et al., *Surveillance of device-associated infections at a teaching hospital in rural Gujarat--India*. Indian J Med Microbiol, 2010. **28**(4): p. 342-7.

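### Covariates for the supporting UTI logistic models are chosen by whether they differ between arms, so screened baseline factors enter only by chance; the arm term and the place of symptoms also need stating.

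*Combined protocol and SAP*

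**What the plan says.** The primary analysis in Section VI is unadjusted: at each time point "we will perform a test of binomial proportions for testing the null hypothesis of no difference between the treatment arms". Everything below concerns the supporting analysis that follows it.

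That analysis starts with a bivariate step: "We will also explore the association between treatment arms and other covariates (symptomatic and demographics factors) using bivariate methods". Symptom variables (fever, pelvic pain, urinary symptoms, antibiotic use) are tested by chi-square against arm. Demographic variables are then tested by t-test or chi-square, in the words "for continuous variables) and chi-square tests (for categorical variables) will be used to compare the two treatment arms". The selection rule comes next: "Variables found to be significant in these bivariate analyses will be included in multivariable analysis using logistic regression".

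The models have two stated purposes. One is prediction: "Logistic regression models will be used to identify significant independent predictors associated with UTI", a sentence that runs on as "occurrence for each treatment arm. We will fit separate logistic regression models for UTI occurrence at the two time points". The other is adjustment: "The logistic model will allow for control of study covariates simultaneously". Section V also relies on adjustment in the analysis to limit confounding.

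The threshold is given once, without saying whether it governs the screen: "A p-value of <0.005 will be used to demonstrate statistical significance". The sample-size paragraph in Section IV.b uses 0.05. No section screens covariates against UTI or lists fixed covariates for these models. Section IV.a does separately intend to look at whether pre-operative antibiotics affect UTI.

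**The concern.** A covariate earns a place in an outcome model by its relation to the outcome. Here it earns its place by its relation to arm, which randomisation makes a matter of chance for anything measured at baseline. A strong predictor of UTI and an irrelevant variable have the same probability of entering. The model described as adjusted would usually contain no demographic covariate, and a screened demographic that really predicts UTI would almost never be identified.

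Two points of wording add to this. If the models are fitted within each arm, they have no arm term and give no adjusted treatment effect to set beside the primary test. If symptoms or antibiotic use may enter, the model conditions on events after randomisation that overlap with the endpoint: Section IV.a counts a patient treated with antibiotics for UTI as a case even without laboratory support.

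**Working it through.** **1. The plan's own figure.** Inputs from Section IV.b: UTI 40% v 20%, alpha 0.05 (two-sided assumed), power 0.84. Without continuity correction, n = [1.960 × √(2 × 0.30 × 0.70) + 0.994 × √(0.40 × 0.60 + 0.20 × 0.80)]² / 0.20² = 90.2, so 91 per arm. With the correction, n = (90.2/4) × [1 + √(1 + 4/(90.2 × 0.20))]² = 99.9, so 100 per arm. The stated size reproduces and is not in dispute. Uncorrected power at 100 per arm is 0.876.

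**2. Chance that no demographic enters.** Section IV.c lists eight baseline items. Each passes a between-arm test with probability about equal to the screening level. If independent, P(none) is:
- at 0.005: 0.995^8 = 0.961 (expected number entering 8 × 0.005 = 0.04)
- at 0.05: 0.95^8 = 0.663 (expected number 8 × 0.05 = 0.4)

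Under assumed correlation between the test statistics (one pair at 0.7, or all pairs at 0.2 to 0.5), simulation gives 0.96 to 0.97 and 0.67 to 0.75.

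**3. Finding a real predictor.** Simulation, 40,000 trials per odds ratio: 100 per arm, UTI 40% v 20%, and a binary predictor with assumed prevalence 30%, in a pooled model with an arm term. The same threshold is used for screen and model. Entries are the proportion of trials in which the predictor is in the model and significant.

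| Odds ratio | Rule, 0.005 | Fixed in advance, 0.005 | Rule, 0.05 | Fixed in advance, 0.05 |
|---|---|---|---|---|
| 2 | 0.0011 | 0.224 | 0.0284 | 0.536 |
| 3 | 0.0034 | 0.674 | 0.0465 | 0.900 |
| 4 | 0.0041 | 0.898 | 0.0504 | 0.981 |

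The rule's figures are close to the product of screening level and fixed-model power: for odds ratio 3, 0.005 × 0.674 = 0.0034 and 0.05 × 0.900 = 0.045.

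**4. Cost to the arm term.** Same set-up, 20,000 trials per odds ratio, power under the rule v with the predictor fixed in advance:

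| Odds ratio | Tested at 0.05 | Gain (points) | Tested at 0.005 | Gain (points) |
|---|---|---|---|---|
| 2 | 0.875 v 0.881 | 0.6 | 0.602 v 0.614 | 1.2 |
| 3 | 0.881 v 0.895 | 1.4 | 0.606 v 0.640 | 3.4 |
| 4 | 0.877 v 0.901 | 2.4 | 0.605 v 0.658 | 5.3 |

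**5. Pooled or within arm?** The predictor sentence ends by referring to each arm, which suggests one model per arm. The next sentence calls only the time-point models separate, which fits a model pooling the arms. The text does not settle it. Selection by arm difference is unsound either way.

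**6. If symptoms may enter a pooled model.** Symptom rates are assumptions; the documents give none. Take 70% symptomatic with UTI and 10% without. Symptom rates by arm are then 0.70 × 0.40 + 0.10 × 0.60 = 0.34 and 0.70 × 0.20 + 0.10 × 0.80 = 0.22. The symptom passes the screen with probability 0.47 at 0.05 or 0.18 at 0.005, because treatment works and not by chance. With it in the model, the arm odds ratio stays at (0.20/0.80)/(0.40/0.60) = 0.375, but the Wald statistic falls from 3.04 to 2.41.

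Simulated arm-term power at 0.05, with selection at 0.05 (0.88 unadjusted):

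| Symptom rate, UTI / non-UTI | Power |
|---|---|
| 90% / 10% | 0.55 |
| 70% / 10% | 0.74 |
| 70% / 20% | 0.82 |
| 50% / 10% | 0.83 |
| 40% / 10% | 0.85 |
| 30% / 10% | 0.87 |

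With selection at 0.005, the 70%/10% case gives 0.82.

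Null case: 30% UTI in both arms, test at 0.05, 70% symptomatic with UTI. If the intervention raises non-UTI symptoms from 10% to 15% or 20%, the error is 0.04 to 0.05. At 30% it is 0.129 with selection at 0.05 and 0.074 with selection at 0.005. With 90% symptomatic in UTI and non-UTI symptoms at 30%, it is 0.24 (selection at 0.05).

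**The case against.** The strongest reply is that little depends on this. The primary test is untouched, the bivariate step is introduced as exploratory, and arm-term power hardly moves. The contrast of 0.3% with 67% is close to a restatement of the screening level. All of that stands, and it limits the weight of the point. It does not rescue the rule: the models have stated purposes and a significance threshold, and the rule cannot meet those purposes.

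The two wording points are ambiguities, not demonstrated errors. The selection sentence directly follows the demographic tests, so a demographics-only reading is natural, although the bivariate step as introduced also covers symptoms. Every symptom figure depends on the wider reading and on assumed rates. Section IV.a counts asymptomatic bacteriuria as UTI, so a high symptom rate among cases may be unrealistic.

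A reader might infer more than the documents support:
- That the trial's main conclusion is compromised. It is not, because the primary test uses no covariates.
- That the plan rules out an adjusted treatment effect. It does not, because the pooled reading is open.
- That symptom adjustment will inflate false positives. This would need symptoms to be eligible and the intervention to cause them in many patients without UTI. Section IV.e allows for some irritation from the plastic cover and lists skin irritation as common with Betadine, but gives no rates.
- That no predictor of UTI could be found. The argument covers only the screened demographics; Section IV.a plans a separate look at pre-operative antibiotics.

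Finally, the chance argument assumes that the randomised groups are kept intact. Section VI names intent-to-treat but also refers to participants treated per protocol. Exclusions could add non-random imbalance, but a between-arm p-value would still not measure relation to UTI.

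**Conclusion.** The selection rule is wrong as written; the two wording points need clarification. Entry at about the screening level follows from 1:1 randomisation with intact groups and needs no assumption about effect sizes. The 96% and 66% figures assume independent variables and change little at 0.005 under correlation. The predictor figures rest on an assumed 30% prevalence, which was not varied, and odds ratios of 2 to 4. The arm comparison loses only about 1 to 5 points of power, so this is a correction that should be made to a supporting analysis and not a threat to the primary result. If symptoms may enter a pooled model, the power loss runs from slight (0.87) to severe (0.55) over the assumed rates. Null error stays near 0.05 unless non-UTI symptoms rise substantially in the intervention arm (about 0.07 to 0.24 when raised from 10% to 30%).

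**What to change.** In Section VI, delete selection by between-arm p-value. At 14 +/- 2 days, and at 24 hours if events allow, fit one logistic model to both arms with an arm term and a short list of baseline covariates fixed in advance. Choose them for expected relation to UTI from those already collected, for example age, BMI, diabetes and menopausal status.

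The documents give no 24-hour UTI rate. At an assumed 5% or 10% there would be 200 × 0.05 = 10 or 200 × 0.10 = 20 events for five terms (arm plus four covariates). State in advance a rule for few events: fewer covariates, or a penalised (Firth) model.

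Include pre-operative antibiotics, in line with Section IV.a, if they are determined before randomisation; Section IV.d records them at the randomisation visit. Keep symptoms and post-operative antibiotic use out of the treatment-effect model. Drainage disruption and catheter-removal method arise after randomisation, so report them by arm or use them only in a labelled sensitivity analysis. Section IV.a calls them possible confounders, so edit that wording to match.

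State that the model supports the primary test of proportions, and label any per-arm predictor model exploratory.

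Cost: wording changes in Sections IV.a and VI. No new data are needed.

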Additional secondary outcomes to be evaluated will include patient discomfort with catheter, tolerability of catheter, length of hospital stay, and number of post-operative evaluations required. A cost-analysis will be performed as a secondary endpoint based on this cost factors (length of hospital stay, readmission, additional clinic/ED visits, antibiotic costs). Costs of hospital days, clinic visits, other appointments, and antibiotics will be standardized for evaluation based on literature for cost analysis in gynecologic oncology literature.

b. Target population. Women undergoing extended surgery lasting >1 hour and requiring urinary catheter will be eligible for enrollment. All patients will have surgery performed by one of the trained Gynecologic Oncologists at the University of Colorado Hospital.

Inclusion criteria will include:

- 1) women 18-89 years of age
- 2) admitted for surgery lasting >1 hour and requiring urinary catheter,
- 3) have normal urine analysis within 24 hours pre-surgery, and
- 4) able to provide informed consent.

Women with dialysis, chronic urinary infection, and current infection will not be eligible to participate. Women who are pregnant or breast feeding will not be included in the study. Men will not be included because of their lower incidence of UTIs compared to our female population.

The null hypothesis is that there will be no difference in UTI rates between the standard of care catheter placement and the sterile protocol placement. If we use the current rates of UTI after catheter placement described above at 40%, we would need to enroll 100 patients per arm (total 200) to see a 50% reduction in UTI rates in the intervention group with an alpha of 0.05 and a power of 0.84. The Gynecologic Oncology services averages around 5 surgical patients who would be eligible for this study per week. We anticipate needing between 10-12 months to complete enrollment.

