c. Study Design and Research Method. We will conduct a single-site Randomized Control Trial (RCT) in order to examine the use of an aseptic protocol for catheter insertion during gynecologic oncology surgeries for quality improvement. This study will take place at the UCH inpatient surgical unit of gynecologic oncology. The catheter protocol for QI will be conducted in the operating room prior to surgery and will not increase prep time or operating room time. Follow-up will be conducted during standard outpatient care visits and will also not increase clinic use time.

The intervention in this study is a controlled aseptic pre-treatment protocol for catheter use in the operating room involving dipping the tip of the catheter into betadine prior to insertion and maintaining catheter in the sterile plastic sleeve during preparation, insertion and post-operatively to avoid excess exposure to the environment. The Physician performing the operation will be responsible for inserting the catheter. Patients with normal UA pre-surgery will be randomized 1:1 to one of two arms prior to surgery:

- 1) Aseptic protocol for catheter insertion using betadine treated catheter and maintaining plastic sleeve on catheter *or*
- 2) SOC catheter insertion in which catheter is inserted right out of package/non-treated catheter.

Prior to study initiation, the PI will train providers on the proper use of the protocol. Catheter insertion procedures will be documented in the operation note following surgery. Compliance will be measured by adherence to both betadine use and maintenance of plastic sleeve. Standard of care practices for infection control are to be conducted by providers on all participants. This includes: hand hygiene, inserting catheters for appropriate indications, remove catheters when no longer needed, maintain a close system keeping bag and tubing below the bladder.

We will collect general patient demographics to assure similarities between the randomized groups. These will include age, race/ethnicity, BMI, insurance type, diagnosis (reason for surgery), history of diabetes, menopausal status, and smoking status. MRN data will be collected in order to pull data directly into the OnCore data management system.

d. Study Procedures

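### The analysis plan's unrestricted p<0.005 conflicts with the alpha of 0.05 and two-way Bonferroni split given elsewhere, so no single rule governs the primary conclusion

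*Combined protocol and SAP*

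**What the plan says.** Three statements bear on the decision threshold.

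- **Section IV.b (Target population), sample-size text:** 100 patients per arm are planned "to see a 50% reduction in UTI rates in the intervention group" from a 40% control rate, "with an alpha of 0.05 and a power of 0.84". It does not say whether the alpha is one- or two-sided.
- **Section VI (Data Analysis Plan), primary outcome:** UTI rates are compared between arms at 24 hours and at 14 +/- 2 days by a test of binomial proportions. "Because we are performing tests at two time points, we will adjust for the multiple comparisons" by Bonferroni. The section gives neither a base alpha nor a per-test level.
- **Section VI, end of the logistic-regression text:** "A p-value of <0.005 will be used to demonstrate statistical significance". The sentence names no analysis to which it applies. The next sentence says which software will be used for all the analyses.

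**The concern.** A Bonferroni split of 0.05 over two tests gives 0.025. The figure 0.005 is neither 0.05 nor 0.025, and nothing in the plan connects it to either. As written, it can be taken as the threshold for every test in the analysis plan, including the two primary ones.

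The threshold decides whether the trial is declared positive. A primary p-value between 0.005 and 0.025 is a success under one rule and a failure under the other. Because the plan does not say which rule governs, the choice could be made after the results are known. The same gap affects covariate selection: variables significant in the bivariate comparisons enter the logistic model, and the level for that step is not clear either.

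**Working it through.** **Inputs.** Control rate 0.40, intervention rate 0.20 (a 50% reduction), n = 100 per arm, alpha 0.05 and power 0.84, all from Section IV.b; 1:1 allocation from Section IV.c; two primary tests from Section VI. Two-sided testing is assumed throughout.

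**Step 1: reproduce the plan's figure.** With mean rate 0.30, z(0.05, two-sided) = 1.960 and z(power 0.84) = 0.994:

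n0 = [1.960·√(2·0.30·0.70) + 0.994·√(0.40·0.60 + 0.20·0.80)]² / 0.20² = 90.2, so 91 per arm without continuity correction.

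With correction: n = (n0/4)·[1 + √(1 + 4/(n0·0.20))]² = 99.9, so 100 per arm.

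The stated 100 per arm is therefore matched by one two-sided test at an unsplit 0.05 with continuity correction. One-sided 0.05 would give 72, or 82 with correction.

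**Step 2: where could 0.005 come from?** 0.05/2 = 0.025. To reach 0.005 from 0.05 by Bonferroni takes 0.05/0.005 = 10 tests; the plan names two.

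**Step 3: power at each level, 100 per arm.** Power = Φ[(d − z·s0)/s1], with s0 = √(2·0.30·0.70/100) = 0.0648 and s1 = √((0.24 + 0.16)/100) = 0.0632. Here d = 0.20 uncorrected, or 0.20 − 1/100 = 0.19 with correction. Exact enumeration of the binomial outcomes is shown beside the formula.

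| Two-sided level | z | Corrected: formula / exact | Uncorrected: formula / exact |
|---|---|---|---|
| 0.05 | 1.960 | 0.840 / 0.844 | 0.876 / 0.880 |
| 0.025 | 2.241 | 0.760 / 0.767 | 0.807 / 0.812 |
| 0.005 | 2.807 | 0.551 / 0.558 | 0.613 / 0.616 |

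Fisher's exact test gives 0.844, 0.769 and 0.559.

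**Step 4: results with opposite verdicts.** Take 40/100 UTIs in the control arm. Two-sided p-values:

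| Intervention UTIs | Corrected z | Fisher | Uncorrected z |
|---|---|---|---|
| 20 | 0.0034 | 0.0032 | 0.0020 |
| 21 | 0.0057 | 0.0055 | 0.0035 |
| 22 | 0.0093 | 0.0091 | 0.0059 |
| 24 | 0.0230 | 0.0226 | 0.0153 |
| 25 | 0.0346 | 0.0341 | 0.0235 |
| 26 | 0.0506 | 0.0502 | 0.0353 |

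The disputed zone is 21 to 24 UTIs by the corrected or Fisher test, and 22 to 25 uncorrected.

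**Step 5: how often the zone is hit under the design effect.** This is the power at 0.025 minus the power at 0.005. Exact: 0.767 − 0.558 = 0.209 corrected; 0.812 − 0.616 = 0.196 uncorrected. That is about one trial in five for a single test.

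**The case against.** The strongest defence is one of scope. The primary test has its own paragraph and its own error control. The plan then turns to exploratory bivariate comparisons and logistic models, and the 0.005 sentence closes that part. Read locally, it sets a stricter bar for many covariate tests, which is a legitimate design preference. That reading is available and cannot be excluded, so the documents show an unresolved scope rather than a proven intention to test the primary outcome at 0.005. It does not remove the problem. The sentence is not limited in words, and if it is confined to the models, the analysis plan has no numeric level at all for the primary tests.

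A reader might also infer that the plan holds three incompatible thresholds: 0.05, 0.025 and 0.005. The documents do not support that. A family-wise 0.05 split over two tests is one coherent rule, so two rules conflict. For p between 0.025 and 0.05 the plan is not really ambiguous, because Section VI requires the adjustment. What remains there is a power shortfall from sizing at the unsplit level. Nor do the documents show that 0.005 is a typing error for 0.05; that is possible, but the sentence would need correcting in that case too.

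Three caveats on the figures stand. The 0.025 is an inference, since Section VI gives no number. The test of proportions is not specified further, so the cut-offs shift by one event with the method. The 40% versus 20% assumption is applied to a single test, and no separate 24-hour rate is given. Section IV.a also frames the primary outcome as UTI within 14 +/- 2 days, so the sponsor should confirm that two primary tests are intended.

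**Conclusion.** The point holds as a conflict between two significance rules: 0.05 with Bonferroni over two time points, and an unrestricted p<0.005 that derives from neither. Under the plan's own design effect, about 20% of trials would give a p-value on which the two rules disagree. If 0.005 does govern the primary tests, a true halving of UTI would be missed about 38–44% of the time (1 − 0.616 to 1 − 0.558), whereas the stated power of 0.84 implies 16%. If 0.025 governs, the stated 0.84 is still too high, though by much less. These sizes assume two-sided tests, 0.05 as the family-wise level, 100 evaluable patients per arm and rates of 40% and 20%. It should be settled before any outcome comparison, because it determines what the trial can conclude.

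**What to change.** Make two edits.

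1. In Section VI, replace the 0.005 sentence with one rule, for example: *The family-wise two-sided alpha for the primary outcome is 0.05; each of the two time-point tests is judged at 0.025 (Bonferroni).* Delete 0.005, or limit it explicitly to the exploratory covariate and logistic analyses. If it is kept, say whether it also applies to the bivariate screening step.
2. In Section IV.b, restate the power at the per-test level: about 0.76–0.77 at 100 per arm by the continuity-corrected method that reproduces 0.84, or about 0.81 uncorrected. Name the method and state that the test is two-sided.

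The cost is two edited sentences and a slightly less favourable stated power. Enrolment, data collection and procedures do not change. Only if the sponsor wants to keep 0.84 at 0.025 would the sample size have to rise, to 119 per arm by the corrected formula (109 uncorrected).

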Infections resulting from health-care complications are the greatest cause of morbidity and mortality in hospitalized patients in the US. [1] Urinary tract infection (UTI) is the most common health care complication following surgery. [2] Rates are high, causing longer hospital stays, readmissions, and antibiotic use. Rates at UCH are near 40%, high compared to the national standard. About 15% of post-op complications result in extended stays or readmissions and costly antibiotic treatments. These infections should be preventable with prophylaxis and pre-treatment protocols but there is no standard protocol at UCH for minimizing the risk of UTI infection. We propose a catheter management protocol in which the catheters are treated with betadine and then inserted while remaining protected within the plastic sleeve, reducing airborne/contact exposures to the catheter. Betadine is a topical antiseptic used in the prevention of infections. It is widely available and a cost-effective intervention. Similar aseptic protocols have been tested and implemented in other countries however we lag behind in having a systematic protocol for reducing the incidence of UTIs complications.[2-4] A study in rural-India found that antiseptic techniques were the best preventable measure for device-related infections.[5] Patients currently receive what will be considered standard of care intra-operative catheter placement which involves placement of catheter in a sterile field, drainage to a closed system and shortest possible duration of catheter placement. We hypothesize that the implementation of a controlled antiseptic protocol to inserting the urinary catheter will reduce UTI rates following surgery.

III. Preliminary Studies/Progress Report:

The Gynecologic Oncology service performs between 15-20 surgeries per week. There are 5 providers who would require training in the protocol. The providers all have similar practice patterns as they pertain to current standard of care catheter placement. Training would be relatively straight forward and protocol adherence is expected to be high. Adherence can be monitored on the service by the principle investigator. Faculty Mentors include [name] who is an assistant professor in the department of Obstetrics and Gynecology at the UCH. He serves as the Principal Investigator for the Gynecologic Oncology Group, a national research consortium. His research has focused on all gynecologic cancer sites and surgical improvements.

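### The cost analysis omits the aseptic protocol's own added cost, a small shift toward the intervention arm in a secondary endpoint

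*Combined protocol and SAP*

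**What the plan says.** The cost inputs are described in two places.

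- **Section VI, Cost-analysis bullet:** "The cost-effectiveness of the interventions will be assessed using hospital stay, readmissions, clinic/ED visits, and antibiotic costs per patient during the study period". Unit costs are to come from the literature. The contrast is then given: "The two groups will be compared in terms of average cost of treatment with a 95% confidence interval using a Bayesian statistic".
- **Section IV.a, additional secondary outcomes:** the cost factors are "length of hospital stay, readmission, additional clinic/ED visits, antibiotic costs". The items to receive a standard unit cost follow: "Costs of hospital days, clinic visits, other appointments, and antibiotics will be standardized for evaluation".

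Other sections bear on what the intervention adds.

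- **Section III:** "There are 5 providers who would require training in the protocol".
- **Section IV.c:** the catheter tip is dipped in Betadine, and the protocol "will not increase prep time or operating room time".
- **Section IV.e:** the plastic cover is one the catheter already has.
- **Sections II and V:** Betadine is called cost-effective and the intervention cheap and easy, without figures.

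No section gives a price for Betadine, supplies, staff time or training. None says that these were left out because they are negligible.

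**The concern.** Section VI presents this analysis as a costing of the two protocols, yet every named input is later health-care use. The resources that differ between the arms by design, the Betadine and the training needed to use the protocol, have no line. A cost present in one arm only and left out of the total shifts the comparison toward that arm.

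The low cost of the intervention is part of the trial's rationale. In the plan as written it is assumed, not entered. If the protocol had no effect on UTI or other care, the expected reported difference in cost would be zero, although the aseptic arm would in fact cost c more per patient.

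**Working it through.** **Inputs from the documents.** Control UTI rate 40%, a 50% relative reduction (to 20%), alpha 0.05, power 0.84, 100 patients per arm (section IV.b); five providers to train (section III). No unit cost is given anywhere.

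**The plan's own figure.** The plan states no figure for the cost analysis. Its sample size reproduces: the two-sided, continuity-corrected formula for 40% versus 20% at alpha 0.05 and power 0.84 gives 100 per arm (91 without the correction). This confirms 0.20 as the design absolute reduction. Nothing else below depends on it.

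**Shift from the omitted item.** Let

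- D = mean downstream cost of one UTI,
- ARR = absolute reduction in UTI risk,
- c = added protocol cost per intervention-arm patient.

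If the downstream saving comes only through UTIs avoided:

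- saving with the listed inputs: S = ARR × D
- saving with the protocol's own cost included: S − c
- shift on the planned contrast: S − (S − c) = c, toward the aseptic arm.

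**Break-even.** The saving is cancelled when c = ARR × D.

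- ARR 0.20 (design): c = 0.20 D, or 20% of the cost of one UTI
- ARR 0.10: c = 0.10 D, or 10%
- ARR 0.05: c = 0.05 D, or 5%

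**Illustration.** The values of D and c are assumptions in currency units, not figures from the documents. The last three columns show c as a percentage of S.

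| D | ARR | S | c = 1 | c = 5 | c = 20 |
|---|---|---|---|---|---|
| 3,000 | 0.20 | 600 | 0.2% | 0.8% | 3.3% |
| 3,000 | 0.05 | 150 | 0.7% | 3.3% | 13.3% |
| 1,000 | 0.20 | 200 | 0.5% | 2.5% | 10% |
| 1,000 | 0.05 | 50 | 2% | 10% | 40% |
| 100 | 0.20 | 20 | 5% | 25% | 100% |
| 100 | 0.05 | 5 | 20% | 100% | 400% |

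The omission matters only toward the bottom of the table. Two statements in the plan keep that region in view. Asymptomatic bacteriuria counts as a UTI (section IV.a), which may lower D. Section V acknowledges many studies that found no difference, so a small ARR is possible.

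**Training share.** If training one provider costs t and all of it is charged to the 100 intervention patients, the share is 5t / 100 = 0.05t per patient. Over a longer horizon it is less.

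**An omission that works the other way.** Laboratory confirmation of positive urine tests is also uncosted. If confirmation costs L and positive tests fall in step with UTIs, restoring it credits the aseptic arm with ARR × L per patient. With an assumed L of 20 to 50 and ARR 0.20, that is 0.20 × 20 = 4 to 0.20 × 50 = 10, which lies within the assumed range of c.

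**The case against.** The strongest reply is that the item is close to nothing. The cover is already on the catheter, section IV.c expects no added preparation or operating room time, and what is left is a Betadine dip and one short training of five people. Section VI also compares a treatment cost that it does not define, which could be read to include supplies. The first part stands: c is probably small. The second does not restore the item. The sentences before that comparison name the inputs, and no section plans to collect or source a cost for the protocol.

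A reader might infer more than the documents support in four ways.

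- **That the whole comparison is biased toward the intervention.** The direction is known for the protocol's own cost only. Omitted laboratory confirmation would push the other way if UTIs fall, so the net sign is unknown.
- **That care for catheter irritation, which section IV.e says the cover may increase, is left out.** The lists are not restricted to UTI-related use. Stays, readmissions and clinic or ED visits are counted per patient over the study period, and other appointments are to be priced. Only irritation care that produces no visit or extra stay would be missed.
- **That the omission should be scaled up as a cost per UTI avoided.** Section VI uses the term cost-effectiveness but defines no such ratio and no costing perspective. The contrast it plans is a difference in mean cost, and on that scale the shift is c.
- **That insertions must be timed.** A sensitivity range answers the question without new data collection in the operating room.

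Whether training belongs in the total depends on the perspective, which the plan does not state. Training is therefore better handled as a sensitivity analysis.

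**Conclusion.** The point holds as a minor one. As written, the cost comparison leaves out the aseptic protocol's own added cost, and for that item the difference in average cost moves by c per patient toward the intervention arm. The size of c cannot be found from the documents and is probably small. At the design effect it would remove the saving only at 20% of the mean downstream cost of one UTI, and at a 5-point reduction at 5%. These thresholds assume that the saving comes only through UTIs avoided and that c is the mean added cost over all patients in that arm. The primary endpoint and the safety assessments are unaffected.

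**What to change.** In sections IV.a and VI:

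1. Add a Betadine and supply unit cost to each intervention-arm patient, and name its source.
2. Report sensitivity analyses with and without a per-patient share of provider training, and with 0 to 5 added minutes of preparation time.
3. For even-handedness, add urine confirmation and culture costs in both arms, and note that this may move the difference in favour of the intervention.

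The cost is a few extra unit costs and a short addition to the cost plan. Enrolment, visits and data collection do not change. The stated saving may come out slightly less favourable.
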